### 6.2 DOSE AND STUDY DRUG ADMINISTRATION

#### 6.2.1 Identity of Study Drug

##### 6.2.1.1 WVE-120101

WVE-120101 will be provided as a lyophilized powder in a clear glass vial for reconstitution for solution for injection. Directions on reconstitution are provided in the Pharmacy Manual.

**Laboratory Code:** WVE-120101

**Chemistry:** WVE-120101 drug substance is the fully neutralized sodium salt of a mixed 2'-*O*-methyl ribonucleic acid/deoxyribonucleic acid oligonucleotide 20-mer containing a prescribed combination of 3'-*O* to 5'-*O* linked phosphodiester and phosphorothioate linkages, the latter of which consist of a prescribed combination of stereodefined *Rp* and *Sp* linkages.

**International Nonproprietary Name (INN):** None

**Molecular Formula:** The empirical formula is: C202H259N82O111P19S13

**Molecular weight:** 6617.05 g/mol (Average)

### **6.2.1.2 Placebo**

Placebo will be 0.9% Sodium Chloride Injection sterile, preservative-free solution administered alone via the IT route. It will be provided in commercially available single-use vials or plastic ampoules. Placebo, as prepared by an unblinded study pharmacist in a dosing solution for injection, will be visually identical in appearance to the WVE-120101 injection solution.

### **6.2.2 Administration of Study Drug and Collection of CSF**

Study drug (WVE-120101 or placebo) will be administered as a single dose followed by multiple doses (3 doses at 4-week intervals). The route of administration will be IT by direct lumbar injection, and the total volume of the injection will be 10 mL. The lumbar puncture will be performed by an appropriately trained individual. Within 1 week prior to the lumbar puncture, a blood sample will be tested locally for platelet count and prothrombin time to confirm that it is safe to proceed with the lumbar puncture ([Section 8.2.6](#)). Patients should not be sedated during administration of study drug. Detailed instructions on the procedure to be used for lumbar puncture are provided in the Study Operations Manual.

Within  $\leq 15$  minutes prior to administration of study drug, CSF samples will be collected for safety assessments ([Section 8.2.7](#)), exposure ([Section 8.3](#)), and PD ([Section 8.4](#)), per the Schedule of Assessments ([Table 1](#), [Table 2](#), and [Table 3](#)). Additional CSF collected will be stored and used for research purposes. No more than 10 mL of CSF total should be collected.

Immediately after each administration of study drug, all patients should be ambulatory and active for approximately 30 minutes postdose. The Investigator should note any subtle weakness or fatigue during this period. In addition, formal physical examinations targeting the neurological system, will be performed at the time points noted in the Schedule of Assessments ([Table 1](#), [Table 2](#), and [Table 3](#)). Any postdose SAEs will be monitored until resolution.

Cerebrospinal fluid samples will only be used by the Sponsor and/or a contracted vendor for research related to the development of treatments for HD and will be stored for a maximum of 10 years. All biological material will be stored and secured in a way that ensures that unauthorized access is prohibited and the samples are not lost, deteriorated, or destroyed accidentally or illegally. Detailed instructions for sample collection, storage, processing, and shipping will be provided in the Laboratory Manual.

## **6.3 TREATMENT COMPLIANCE**

Provided that a patient attends the clinic visits, treatment non-compliance is not expected to be an issue. Thus, every attempt will be made to ensure regular visits by the patient to the clinic per the study schedule. Investigative staff will make every effort to contact patients who miss visits in order to obtain as much follow-up information as possible.

## **6.4 MANAGEMENT OF CLINICAL SUPPLIES**

### **6.4.1 Study Drug Packaging and Storage**

WVE-120101 will be supplied by the Sponsor as a lyophilized powder in clear glass vials. Sterile saline (placebo) will be supplied in commercially available single-use vials or plastic ampoules.

All study drugs will be transported, received, stored, and handled in accordance with the container or product label, the instructions supplied to the pharmacy, relevant institution's Standard Operating Procedures (SOPs), and applicable regulations. Appropriate storage and transportation conditions will be maintained for the study drug from the point of manufacture up to delivery of the study drug.

Study drugs will be stored at 2°C to 8°C in a locked area accessible only to the pharmacy personnel until reconstitution. WVE-120101 reconstituted and diluted solution for injection contains no preservatives and should be administered without delay or within 4 hours of reconstitution.

Partially used, unused, or damaged vials should be disposed according to Sponsor instructions.

Details on reconstitution and administration are provided in the Pharmacy Manual and Investigator's Brochure (IB).

### **6.4.2 Study Drug Accountability**

The Investigator will maintain accurate records of receipt of drug supplies, including dates of receipt. In addition, accurate records will be kept regarding when each treatment is administered, which patients received treatment, and the name of the personnel administering the treatment. Reasons for departure from the expected treatment regimen must also be recorded. Only trained site staff are permitted to treat study patients. A study monitor will review the accountability records onsite.

## **6.5 OTHER SUPPLIES**

The study sites will be provided with the IB, Study Operations Manual, Pharmacy Manual, Imaging Manual, Laboratory Manual, laboratory kits, and other materials, as appropriate.

## **7 BLINDING**

### **7.1 BLINDING AND RANDOMIZATION**

This is a double-blind and placebo-controlled randomized study. The treatment blind will not be broken until the end of the study, except in the case of emergency ([Section 7.2](#)). The Sponsor and contract research organization (CRO) staff directly responsible for the conduct of data collection for the study, the Investigator, and study center staff will be blinded to treatment for the duration of the study until such time that all discrepancies in the clinical database are resolved (ie, at the time of the database lock).

The randomization scheme will be assigned by an IXRS, which will send notifications of the treatment assignment to the designated pharmacy personnel.

The pharmacy personnel will be unblinded to prepare doses of WVE-120101 or placebo to ensure that the clinical site staff responsible for administering study drug and conducting assessments per the protocol, and the patient, remain blinded to study treatment. In addition, a clinical research associate will be unblinded to perform drug vial accountability and oversee the shipping and inventory of study drug.

## **7.2 BREAKING THE BLIND**

A patient's treatment assignment will not be broken until the end of the study except in the event that medical treatment of the patient depends on knowing the study treatment the patient received. If the Investigator feels they need to break the blind in the case of medical emergency, they can do so via the IXRS system.

In addition, certain Sponsor or CRO staff members may be unblinded to the applicable patient's treatment code as required for regulatory reporting of SUSARs.

Reasons for treatment unblinding must be explained clearly and justified in the eCRF. The date on which the code was broken, together with the identity of the person responsible for breaking the blind, must also be documented in the patient's source documents. The unblinded treatment information will not be disclosed to anyone who does not need to know the information. In consultation with the medical monitor and the Sponsor, the patient may be withdrawn from the study if the blind is broken.

## **8 METHODS OF ASSESSMENT AND ENDPOINTS**

### **8.1 PRESCREENING ASSESSMENTS**

WVE-120101 is specifically designed to treat HD patients who carry the U isoform of the intended SNP on the same allele as the pathogenic CAG expansion ( $\geq 36$  repeats). If documentation of heterozygosity at SNP1 is not available, patients must have a blood sample taken at a Prescreening Visit to enable patient eligibility assessment based on these criteria using 3 separate methods:

The number of CAG repeats will be confirmed via polymerase chain reaction (PCR). Subsequently, Sanger sequencing will be performed to determine heterozygosity at the targeted SNP.

Only samples for which heterozygosity and required CAG repeats have been confirmed will undergo further testing using a long-read sequence analysis to determine whether the T isoform of SNP1 is present on the same allele as the pathogenic CAG expansion. Long-read sequencing technology will be performed by a central laboratory using a CE-marked genetic sequencer (Pacific Biosciences RS II System).

Patients confirmed to carry the T isoform of SNP1 on the same allele as the pathogenic CAG expansion will be qualified to undergo further screening for confirmation of eligibility.

Investigators and patients will be advised only as to whether the patient meets the prescreening criteria and will not be provided with specific genetic test results (eg, number of CAG repeats).

All blood samples will be sent to central laboratories for processing, analysis, and verification. All biological material will be stored and secured in a way that ensures that unauthorized access is prohibited and the samples are not lost, deteriorated, or destroyed accidentally or illegally. Detailed instructions for sample collection, storage, processing, and shipping will be provided in the Study Operations Manual.

## 8.2 SAFETY ASSESSMENTS

The safety assessments will include the following:

- Adverse events ([Section 9](#))
- Medical history and demographics
- Prior and concomitant medications
- Physical examinations (including neurological and psychiatric)
- Vital signs
- 12-lead ECGs
- Clinical laboratory evaluations (including clinical chemistry, hematology, and urinalysis)
- Magnetic resonance imaging ([Section 8.6](#))
- Cerebrospinal fluid sample evaluations (cell count and total protein)
- Suicidality assessment
- Pregnancy testing

Any abnormal laboratory test results (hematology, clinical chemistry, or urine) or other safety assessments (eg, vital sign measurements, C-SSRS), including those that worsen from Screening (Visit 2), that are felt to be clinically significant in the medical and scientific judgment of the Investigator are to be recorded as AEs or SAEs.

### 8.2.1 Medical History and Demographics

A general medical history will be obtained at the Screening Visit. Investigator assessment of past medical history at Screening will include information regarding any significant medical, surgical, psychiatric, and/or neurological conditions and treatments.

Whether the patient is diagnosed with Stage 1 or Stage 2 HD, treatments received, and other details about this condition will be recorded.

Demographic data will include date of birth, sex, ethnic categorization, and race.

### **8.2.2 Prior and Concomitant Medications**

Use of all concomitant medications from 6 weeks before the Screening Visit to the end of the patient's participation in the study will be recorded in the patient's eCRF. The minimum requirement is that the drug name, dose, indication, and the dates of administration are to be recorded. This will include all prescription drugs, herbal products, vitamins, minerals, and over-the-counter medications. Any changes in concomitant medications will also be recorded in the patient's eCRF.

Any concomitant medication deemed necessary for the welfare of the patient during the study may be given at the discretion of the Investigator. However, it is the responsibility of the Investigator to ensure that details regarding the medication are recorded in full in the eCRF.

### **8.2.3 Physical Examination**

A physical examination will be performed at the time points noted in the Schedule of Assessments ([Table 1](#), [Table 2](#), and [Table 3](#)).

At Screening, the full physical examination will include (but is not limited to) an examination of skin; head, eyes, ears, nose, throat; respiratory; cardiovascular; gastrointestinal; endocrine, metabolic; blood, lymphatic; musculoskeletal, psychiatric, and neurologic (including mental status, cranial nerves, motor system, reflexes, coordination and gait, and sensory system) systems.

Through 4 hours postdose (and up to 24/48 hours postdose following administration on Day 1), a targeted physical exam to assess potential motor effects will be performed. This exam will include a neurologic examination with special attention to the motor system, upper and lower extremity measures of strength, tone, reflexes, and ambulation.

At all other time points, the physical exam must include (at a minimum) head, eyes, ears, nose, throat, respiratory, cardiovascular, gastrointestinal, musculoskeletal, psychiatric, and neurologic). Other systems should be evaluated as appropriate.

Physical findings will be recorded in the eCRF and source documents.

### **8.2.4 Vital Signs**

Blood pressure (systolic and diastolic), temperature, and pulse will be measured by medically qualified personnel at the time points described in the Schedule of Assessments ([Table 1](#), [Table 2](#), and [Table 3](#)), and recorded in the eCRF and source documents. Vital signs measurements will be taken as per standard site practice, after the patient has been resting quietly (either lying flat or sitting, whichever is most appropriate for the condition of the patient) for a period of at least 3 minutes. As feasible, the same position (either sitting or lying) should be used for all subsequent vital sign measurements during the study for an individual patient. If the initial reading is high, the measurements will be repeated twice and the average of the 3 readings will be used.

The patient's height and weight will be measured at the time points described in the Schedule of Assessments ([Table 1](#), [Table 2](#), and [Table 3](#)), and recorded in the eCRF and source documents.

### 8.2.5 12-Lead ECG

Computerized, good quality, 12-lead ECGs will be recorded in triplicate at the time points described in the Schedule of Assessments (Table 1, Table 2, and Table 3). Recordings will be obtained in the supine position after the patient has rested comfortably for  $\geq 5$  minutes.

The ECG tracing will be submitted and read by a centralized reviewer (details will be provided in the ECG Study Manual). The following should be recorded on the trace and eCRF: whether the ECG is normal or abnormal and, if deemed abnormal, whether the abnormality is clinically significant or not clinically significant and note the abnormality.

### 8.2.6 Clinical Laboratory Evaluations

Clinical laboratory safety testing will be collected at the time points described in the Schedule of Assessments (Table 1, Table 2, and Table 3) and recorded in the eCRF and source documents. A blood sample will be tested locally within 1 week prior to the lumbar puncture to determine platelet count and prothrombin time, and thereby confirm that it is safe to proceed with the lumbar puncture. Other safety laboratory samples will be analyzed at a central laboratory. Local testing on these samples may be conducted as clinically indicated.

The parameters to be assessed are presented in Table 5.

**Table 5 Clinical Laboratory Parameters**

Hematology	Clinical chemistry	Urine dipstick
Complete blood count, including: 
 
• White blood cell count (with differential)
 
• Red blood cell count
 
• Hemoglobin
 
• Hematocrit
 
• Platelet count
 
• Reticulocyte count
 
• Mean corpuscular volume
 
• Mean corpuscular hemoglobin
 
• Mean corpuscular hemoglobin concentration
 
 Activated partial thromboplastin time Prothrombin time C-reactive protein Fibrinogen Complement	Sodium Potassium Chloride Bicarbonate Blood urea nitrogen Creatinine Creatine phosphokinase Alanine aminotransferase Aspartate aminotransferase Alkaline phosphatase Bilirubin	Urinalysis

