  - m On Day 1, sentinel patients will have blood samples for PK analysis collected predose, 30 minutes ( $\pm 5$  minutes), 1, 2, 4 hours ( $\pm 15$  minutes), 12 hours ( $\pm 2$  hours), 24 hours and 48 hours ( $\pm 4$  hours) postdose. All other patients will have blood samples for PK analysis collected predose and 30 minutes ( $\pm 5$  minutes), 1, 2, 4 hours ( $\pm 15$  minutes), 12 hours ( $\pm 2$  hours), and 24 hours ( $\pm 4$  hours) postdose on Day 1. On Day 112, all patients will have blood samples collected for PK analysis predose and 1, 2, and 4 hours ( $\pm 15$  minutes) postdose. On all other dosing days, PK samples will be collected predose only. On non-dosing days noted, PK will be collected once.
  - n Blood sample for assessment of antibodies to WVE-120101 will be obtained predose (within 1 week prior to injection) or on non-dosing days, as indicated.
  - o On dosing days, CSF sample will be collected  $\leq 15$  minutes prior to study drug administration. No more than 10 mL of CSF total should be collected. CSF samples must be tested locally for safety for the following parameters: total protein, glucose and cell counts (white blood cell counts with differential) on all noted visits.
  - p Immediately after study drug administration, patients should be active for approximately 30 minutes postdose.
  - q All patients will remain in the clinic and have AEs and concomitant medications recorded through 24 hours postdose. In addition, 2 sentinel patients will remain in the clinic and have AEs and concomitant medications recorded throughout the 48-hour postdose period.
  - r This lumbar puncture is optional for patients who terminate early.

**Table 2 Schedule of Assessments for Patients Participating in Both the single and Multiple Dose Portions of the Study (32 mg Cohort)**

Visit	Pre-Screening a	Screening b	Double-Blind Treatment (Single Dose)		Sentinel Patient Follow-up	Follow-up	Double-Blind Treatment (Multiple Dose)			Follow-up		
	1	2	3	4	5	6	7 c	8	9	10 or ET	11	12
Week		-4 to 0	0	0	0	2	4	8	12	16	24	26
Study Day (Visit Window, if applicable) Event/Assessment		Day -28 to -1	Day -6 to Day 1 (Baseline)	Day 2 (24 ± 4h postdose)	Day 3 (48 ± 4h postdose)	Day 14 (±2)	Day 28 (±3)	Day 56 (±3)	Day 84 (±3)	Day 112 or ET (±5)	Day 168 (±5)	Day 182(EOS) (±5) d
Pre-dose/Non-dosing Days												
Patient informed consent form (ICF) Signed	X	X										
Inclusion/exclusion criteria		X	X				X					

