### 8.2.7 Cerebrospinal Fluid Safety Lab

A CSF safety laboratory sample obtained at the times noted on the Schedule of Assessments (Table 1, Table 2, and Table 3) will be evaluated at a local lab. The following parameters will be assessed: total protein, glucose, and cell counts (white blood cell counts with differential).

Samples will only be used by the Sponsor and/or a contracted vendor for research related to the development of treatments for HD and stored for a maximum of 10 years. All biological material will be stored and secured in a way that ensures that unauthorized access is prohibited and the samples are not lost, deteriorated, or destroyed accidentally or illegally. Detailed instructions for sample collection, storage, processing, and shipping will be provided in the Laboratory Manual.

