#### **10.9.6 Cerebrospinal Fluid Safety Lab**

Cerebrospinal fluid safety lab values and changes from baseline over time will be summarized for each continuous clinical laboratory parameter. Shift tables showing the pattern of change from baseline to each postbaseline visit will be presented.

All data will be presented by patient in data listings.

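### CSF glucose is tabulated at every scheduled lumbar puncture with no paired blood glucose, so a single patient's change cannot be separated from a change in blood sugar

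*Combined protocol and SAP*

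**What the plan says.** Section 8.2.7 defines the CSF safety panel: "The following parameters will be assessed: total protein, glucose, and cell counts (white blood cell counts with differential". The CSF footnotes to the schedules (o in Tables 1 and 2, n in Table 3) make it compulsory at every CSF visit: "CSF samples must be tested locally for safety for the following parameters: total protein, glucose and cell counts". The overview list in Section 8.2 is shorter, "Cerebrospinal fluid sample evaluations (cell count and total protein", and leaves glucose out.

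For the analysis, Section 10.9.6 states: "Cerebrospinal fluid safety lab values and changes from baseline over time will be summarized for each continuous clinical laboratory parameter". It adds: "Shift tables showing the pattern of change from baseline to each postbaseline visit will be presented".

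For blood, Section 8.2.6 states: "The parameters to be assessed are presented in Table 5". The chemistry column of that table is "Sodium Potassium Chloride Bicarbonate Blood urea nitrogen Creatinine Creatine phosphokinase Alanine aminotransferase Aspartate aminotransferase Alkaline phosphatase Bilirubin". Apart from the local platelet count and prothrombin time before each puncture, Section 8.2.6 sends safety bloods to a central laboratory, with one allowance: "Local testing on these samples may be conducted as clinically indicated".

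**The concern.** CSF glucose moves with blood glucose, so a CSF value is normally read against a blood value taken at about the same time. The plan collects and tabulates the first without the second.

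The consequence falls mainly on the individual patient. Under Section 8.2 the investigator, blinded, must decide whether an abnormal safety result is clinically significant and should be recorded as an adverse event. Under Section 9.2.2 the investigator then judges its relationship to study drug, and relatedness enters the stopping criteria in Section 4.3.4. With CSF glucose alone, a low value could reflect low blood sugar or a process in the CSF, and a normal-looking value taken when blood sugar was high could conceal a relative fall.

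The sponsor's own toxicology makes the measure relevant. Section 1.3 reports treatment-related mononuclear infiltrates in monkeys, mainly at the meninges and epineurium bordering the spinal cord.

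**Working it through.** **1. How often CSF glucose is measured.** Counting the CSF row of each schedule:
- Table 1 (2 to 16 mg): Days 1, 28, 56, 84, 112, 140, 196 = 7.
- Table 2 (32 mg): Days 1, 28, 56, 84, 112, 168 = 6.
- Table 3 (multiple-dose portion only; 2 to 16 mg days): Days 56, 84, 112, 140, 196 = 5.

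**2. Whether blood glucose is collected.** Table 5 has 14 haematology and coagulation entries, 11 chemistry entries and urinalysis, 26 in all. None is glucose. Urinalysis is listed without components and is not a blood measure. No schedule row or footnote adds a blood glucose, a fasting condition or a CSF/blood ratio.

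**3. Whether a paired value could be recovered from existing samples.** Not reliably. CSF is drawn within 15 minutes before dosing, but the starred notes to Tables 1 to 3 allow predose laboratory blood up to a week earlier. At Day 196 (Day 168 in the 32 mg cohort) only platelet count and prothrombin time are required. The local-testing allowance is discretionary and names no analyte.

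**4. Size.** The protocol states no figure here to reproduce. Let r be the correlation between a patient's change in CSF glucose and the change in blood glucose over the same two visits. The documents give no r, so a range of 0.3 to 0.9 is assumed.

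Share of variance due to blood glucose = r². The SD left after accounting for it is the raw SD times √(1 − r²), both for an individual's change and for a group contrast.

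Unadjusted 95% half-width of active minus placebo, in SD units = t(0.975, n₁+n₂−2) × √(1/n₁ + 1/n₂):
- 9 v 3 (one cohort): 2.228 × 0.667 = 1.49
- 9 v 15 (one dose v placebo pooled over five cohorts): 2.074 × 0.422 = 0.87
- 45 v 15 (all doses v pooled placebo): 2.002 × 0.298 = 0.60

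| r | share r² | 9 v 3 | 9 v 15 | 45 v 15 |
|---|---|---|---|---|
| none | – | 1.49 | 0.87 | 0.60 |
| 0.3 | 9% | 1.42 | 0.83 | 0.57 |
| 0.5 | 25% | 1.29 | 0.76 | 0.52 |
| 0.7 | 49% | 1.06 | 0.62 | 0.43 |
| 0.9 | 81% | 0.65 | 0.38 | 0.26 |

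The adjusted figures ignore the degree of freedom spent on the covariate and chance imbalance in it, so they are slightly optimistic. Blood glucose would account for more than half the variance only if r² > 0.5, that is r above about 0.71.

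**The case against.** The strongest reply is that the trial is randomised, double-blind and controlled by intrathecal placebo. Blood sugar is balanced between arms on average, so omitting it costs precision and does not bias the comparison. Section 2.1 gives the placebo group the task of separating drug effects from those of the puncture and injection, and Section 10.9 summarises safety by treatment group. This stands. A reader might infer that CSF glucose changes cannot be attributed to drug at all; at group level the documents do not support that. The contrast is available but imprecise, as it is for every safety measure with 3 placebo patients per cohort. It also needs the placebo patients in the tables: read literally, the Safety population in Section 10.3.1 is restricted to recipients of WVE-120101, which must be reconciled with Section 10.9.

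A reader might also infer that these changes mostly reflect blood sugar. That needs a correlation above about 0.71, which the documents do not supply. Nor would a paired blood glucose isolate a procedure effect, because every patient is punctured and no arm goes without.

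A further reply is that infection or meningeal reaction would show elsewhere. The same CSF sample yields white cells with differential and total protein. Table 5 adds C-reactive protein and a blood differential, and temperature and neurological examinations are scheduled. This also stands: an ambiguous glucose result is not a missed reaction.

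Two points stand in part. Exclusion 13 covers endocrine or metabolic conditions that would interfere with assessments, but it rests on investigator judgement and does not control ordinary variation between visits. The Laboratory Manual and Study Operations Manual were not available and might call for a paired draw. Even so, Table 5 and Section 10.9.6 define what is collected and tabulated, and they contain no such value.

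**Conclusion.** The concern holds in a limited form. CSF glucose is a compulsory safety measure with change-from-baseline and shift tables, and no blood glucose is planned beside it. For a single patient, a change or shift cannot be separated from a concurrent change in blood sugar, and randomisation does not help there. For groups the loss is one of precision: between almost nothing (0.87 to 0.83 SD for 9 v 15 at r = 0.3) and more than half the interval width (0.87 to 0.38 SD at r = 0.9). These figures rest on the assumed range of r and on pooling placebo across cohorts.

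No stated sample size or error rate is affected, and the rest of the CSF panel remains informative. This is a worthwhile low-cost improvement, not a threat to the primary safety assessment.

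**What to change.** - **Collection.** In the CSF footnotes of Tables 1, 2 and 3 (o, o and n) and in Section 8.2.7, add one blood glucose drawn close in time to each CSF sample, including Day 196 (Day 168 in the 32 mg cohort). Adding glucose to Table 5 alone would not achieve this, because that blood may be drawn up to a week earlier.
- **Laboratory.** Test it at the same local laboratory as the CSF, and state this in Section 8.2.6 and Table 5 as an exception to central testing.
- **Analysis.** In Section 10.9.6, summarise the CSF/blood glucose ratio and its change from baseline by treatment group, alongside raw CSF glucose. Keep the raw glucose shift table, since a shift table on the ratio would need category limits that are not defined. List the paired values by patient.
- **Consistency.** Align the CSF list in Section 8.2 with Section 8.2.7 by adding glucose.

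The cost is one routine assay per puncture, a same-day blood draw at visits where the blood could otherwise have been taken earlier, a few lines of text and one table. Dosing, eligibility and sample size are unchanged. Some noise will remain because blood and CSF glucose are not perfectly in phase.
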